Subjects receive placebo or 15mg of mirtazapine prior to the scan. This dose of mirtazapine was chosen because this is the lowest dose that has a clinical effect for depression, and based on our preliminary data that some subjects had sedation after 30mg of mirtazapine. For each subject scans will be repeated after 7 days, with the order of administration randomized across subjects.

Subjects will be monitored for side effects, behavioral effects, and vital signs will be obtained for up to 8 hours after the dose when subjects who have vital signs within normal limits and no side effects will be released. Subjects will return 7 days later for identical procedures. This allows 5 half-lives of mirtazapine between scans to minimize carry-over effects.

The maximum number of hours for subjects to complete the entire research study is about 23 hours.

Face-to-Face Interviews/ Surveys

Cocaine Craving Scale: is a 3-item instrument which asks about participant perceptions of their cocaine craving. Participants are asked to rate their current, past week, and worst craving in the past week on a scale ranging from 0 (not at all) to 100 (extremely), using a visual analog scale.

Cocaine Selective Severity Assessment: The Cocaine Selective Severity Assessment (Kampman, 1998) measures early cocaine abstinence signs and symptoms. It is a reliable and valid measure of cocaine abstinence symptoms, and a useful predictor of negative outcomes in cocaine dependence treatment, and requires approximately 5 minutes to complete.

Drug Effect Questionnaire (DEQ): This form utilizes a visual analog scale to measure potential side-effects of mirtazapine. This form is will be administered at different intervals after administration of mirtazapine before and after the fMRI session.

Medical and Laboratory Evaluation:

All subjects will undergo an electrocardiogram (EKG), on all MRI scan session days Urine drug screens will be obtained upon initial evaluation, and on each day of behavioral testing. Urine pregnancy tests will be performed on all female subjects on each day of behavioral and MRI testing. A positive pregnancy test will immediately terminate the subject from additional study procedures.

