Monitoring for Drug Usage: Drug and alcohol usage will be monitored by obtaining urine and expired air samples on each day of the study. Subjects will be rescheduled if they have a positive alcohol breathalyzer. Cocaine-dependent subjects will not be excluded from participation if urine testing for marijuana or cocaine is positive on the morning of each test day, since this would eliminate a significant majority of subjects. Presence or absence of marijuana or cocaine in urine on testing days will be included as a covariate in the statistical analyses. Healthy control subjects will be required have negative urine screen on all study session days and will be excluded if there is a positive screen.

Standardized assessments include the following behavioral tasks:

Iowa Gambling Task [Bechara et al. 1997].

This is a computerized version of the original gambling task in which subjects are asked to choose between four decks of cards which result in theoretical monetary rewards at different rates. Each deck (labeled A, B, C, and D) contains 60 cards. Subjects must make 100 choices over the testing session. Healthy controls are able to determine that two decks of cards on the short-term lead to minimal monetary rewards but over the long-term are more advantageous due to large losses in the other two decks of cards. This task has been able to differentiate between patients with frontal cortical lesions and controls [Bechara, Damasio, Tranel, and Damasio 1997; Bechara et al. 1998], and drug users and controls [Bechara et al. 2001]. The task takes about 15 minutes to complete. Scoring for the Iowa Gambling Task is based on the total number of cards selected from the advantageous minus the disadvantageous decks across five blocks of 20 cards each. The net score of cards selected ((C+D)-(A+B)) in each of the five blocks will be used as a measure of impulsivity.

The Kirby Monetary Choice Delay Discounting Questionnaire:

The monetary-choice questionnaire was based on one developed by Kirby et al (1999). Participants were presented a fixed set of 27 choices between smaller, immediate rewards (SIRs) and larger, delayed rewards (LDRs). For example, on the first trial participants were asked, "Would you prefer \$54 today, or \$55 in 117 days?" The participant indicated which alternative he or she would prefer to receive by circling the alternative on the questionnaire. The order was

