a. The Go-NoGo (Response Inhibition) fMRI task (- - -) is a rapid presentation stochastic event-related fMRI design containing two levels of difficulty. The stimulus array consists of two boxes containing (a) diagonal lines in the same direction for Go trials, (b) diagonal and horizontal lines for Easy NoGo trials, and (c) diagonal lines in opposite directions for Hard NoGo trials. The two boxes are presented simultaneously side by side on the screen for 500 ms, followed by a blank screen jittered randomly for 1900 ms, 2100 ms, or 2300 ms. NoGo trials occur randomly throughout the run. One run lasts approximately 10 min and consists of 224 trials: 168 (75%) Go; 28 (12.5%) Easy NoGo; and 28 (12.5%) Hard NoGo. Easy NoGo activation is defined as the parameter estimate of the Easy NoGo stimuli on which the subject responded correctly minus the parameter estimate of the Go stimuli on which the subject responded correctly. fMRI activation is similarly defined for the Hard NoGo contrast of interest. The difference in activation (Hard NoGo minus Easy NoGo) will also be analyzed.

b. The Attentional Bias (modified Stroop task) fMRI task is a widely-used implicit task in which the subject is presented with words printed in color, and asked to discriminate the color of each stimulus and to ignore the meaning of the words. There are ten cocaine-related words (e.g., "cocaine", "crack"), and ten neutral words consisting of household features (e.g., "table", "kitchen"). The word sets are matched in length or frequency of use using typical procedures. Subjects are instructed that words written in different colors (blue, green, or red) will be presented on the screen, one after the other, and that their task is to indicate the color in which the word is written as quickly and as accurately as possible, ignoring the meaning of the word itself. A new word is presented 500 ms after a response (or 500 ms after the timeout of 3 sec). In this block design fMRI protocol, a block (60 s) of neutral words alternates with a block (60 s) of cocaine words and each fMRI run is approximately 10 min. Subjects first respond to a practice sequence (50 trials) of letter strings (e.g., HHHH). Within each Stroop task, the program randomly determines the presentation order of words and colors for each participant under the constraint that the same color does not appear on two consecutive trials.

Statistical Analyses. Power Analysis: fMRI Power Analysis.

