The power analysis for fMRI data (second level "Random Effects" SPM8 between-group general linear model analysis) used the model and equations in the papers by Friston et al.; brain signals are modeled by continuously distributed Gaussian kernels of random height and of width (f) in proportion to W , where W is the smoothness of the random field.

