The standard deviation (σ), of the kernel corresponds to the height (i.e., intensity) of the measured signal. The kernel is then convolved with an uncorrelated random process representing noise. The new process representing signal+noise has zero mean and variance $1 + \sigma^2$. We estimate signal height to be the voxel t value which is determined by the desired effect size (d) (7, formula 2.5.4, p.67). In this analysis, we have conservatively assumed that the degrees of freedom are reduced by the presence of up to four additional potential covariates (e.g., demographic and/or behavioral variables). We used the observed values of field smoothness (W), underlying signal width (f) prior to smoothing, and 3D brain volume (R) from our pilot event-related Go-NoGo fMRI study (see Preliminary data). Based on the observed effect size ($d = 0.83$) for the second-level (Random Effects) within-group activation of mirtazapine vs. placebo in the event-related fMRI pilot study for Go-NoGo, we have calculated the predicted effect size $d = 0.57$ for the between group comparison using the conversion formula in Cohen,⁷ formula 2.5.6, p.71), but this is probably inflated due to the small sample. Therefore for fMRI power analysis we have conservatively used a more modest effect size of 0.25. For an effect size $d = 0.25$ and Random Field Theory family-wise error-corrected 2-tailed $\alpha = 0.05$ at the cluster level of inference, observed 3D search volume = 188579 voxels, observed field smoothness $W = [4.9\ 4.9\ 4.3]$ voxels (FWHM), width of signal prior to smoothing (relative to W) $f = 0.909$ (calculated based on observed width after smoothing and known spatial smoothing kernel), and minimum cluster spatial extent $k = 23$ voxels that was computed to achieve the above α at a cluster-defining voxel height threshold $u = 4.5$, we have calculated that a sample size of 25 subjects in each group would achieve a power of at least 89 percent for the event related Go-NoGo fMRI between-group activation comparison. We expect the power to be greater than this for the block design Attentional Bias fMRI study, since we have observed effect sizes greater than 0.83 for the within-group activation of mirtazapine relative to placebo in the pilot Attentional Bias fMRI study, and block design is generally more efficient than event-related design, leading to higher t values given the same residual error variance.

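### No order or session term is named for the crossover drug-minus-placebo comparisons: a low-priority, nearly free gain in precision, not a validity defect

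*Combined protocol and SAP*

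**What the plan says.** Study Procedures, question 6, describes a two-period crossover. Subjects are scanned after placebo or mirtazapine, "with the order of administration randomized across subjects", and "Subjects will return 7 days later for identical procedures". The 7-day gap is justified by drug half-life, as a guard against carry-over. The second hypothesis of Aims 1 and 2 is that the reduction in activation after mirtazapine is greatest in one of four cells of 25 (cocaine-dependent or control, Ser23 or Cys23).

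The second-level model is described only in the fMRI Power Analysis, as an "SPM8 between-group general linear model analysis". The terms mentioned for the analyses are:

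- Monitoring for Drug Usage: "Presence or absence of marijuana or cocaine in urine on testing days will be included as a covariate in the statistical analyses".
- fMRI Power Analysis: an allowance for "up to four additional potential covariates (e.g., demographic and/or behavioral variables".
- Exploratory Aim: other receptor polymorphisms that may need to enter as covariates.

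No order, session, period or sequence term appears. The text does not say whether order is blocked within the four cells.

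**The concern.** In a two-period crossover, anything that changes the task contrast from the first to the second session (practice, habituation to the scanner) enters the drug-minus-placebo score with opposite signs in the two orders. Washout does not deal with this, because it is not carry-over. Without an order term the shift stays in the residual and widens every between-cell comparison of drug response. The trial already randomises order, so one regressor would remove it. With 25 subjects per cell, lost precision is worth recovering if recovery is nearly free. A reader also cannot tell from the text whether the analysis will use the randomised order, and naming the term beforehand prevents a choice between models after the results are seen.

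**Working it through.** **The plan's own figure.** The fMRI Power Analysis states at least 89% power at d = 0.25 with 25 per group. The cluster extent threshold of 23 voxels reproduces with a t-field on 25 + 25 − 2 − 4 = 44 df (tail probability 0.0234 against 0.025). The 89% does not reproduce exactly. Different readings of the field and height threshold give 60%, 85.7% or 94.9%, which bracket it, so it is not called wrong. The figures below are therefore for a single test in one region, two-sided 5%, and are not the plan's cluster-level power.

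**Inputs.** Cells of 25 and four cells (Study Procedures, question 6). The planning effect is d = 0.25 ("conservatively used a more modest effect size of 0.25"). The pilot-derived d = 0.57 is a figure of which the plan says "this is probably inflated due to the small sample". The session effect g is not in the documents and is assumed to lie between 0 and 0.75.

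**Model.** D = cell mean + g·s + e, where D is the drug-minus-placebo score, s = +1 or −1 for order, and SD(e) = 1. Without the term, Var(D) = 1 + g² and the effective n per cell is 25/(1 + g²). Power comes from the noncentral t with noncentrality d·√(25/2)/√(1 + g²). On four pooled cells, df = 100 − 4 = 96.

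| g | 1 + g² | effective n | power, d = 0.57 | power, d = 0.25 |
|---|---|---|---|---|
| 0.1 | 1.010 | 24.8 | 51.0% | 14.0% |
| 0.2 | 1.040 | 24.0 | 49.9% | 13.8% |
| 0.25 | 1.0625 | 23.5 | 49.0% | 13.6% |
| 0.5 | 1.250 | 20.0 | 43.0% | 12.3% |
| 0.75 | 1.5625 | 16.0 | 35.8% | 10.8% |
| any, with the term (order balanced, 95 df) | 1 | 25 | 51.4% | 14.1% |

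The largest gain at d = 0.25 is 14.1 − 10.8 = 3.3 points. In a two-group model (48 df), power at d = 0.57 without the term is 48.3%, 42.3% and 35.2% at g = 0.25, 0.5 and 0.75, against 50.6% with it.

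**Cost of the term.** The degree of freedom itself is trivial: going from 95 to 90 df moves power at d = 0.57 from 51.40% to 51.35%. With a simple randomisation list, order overlaps with cell by chance. This inflates the variance by roughly 1/96 with four cells pooled (1.06% on average) and 1/48 in a 25-v-25 model (about 2.1%). At g = 0 and d = 0.57:

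- Four cells pooled: 51.4% falls to 51.0%, a loss of 0.4 points; break-even g = √0.0106 ≈ 0.10.
- 25 v 25: 50.6% falls to 49.8%, a loss of 0.8 points; break-even g = √0.021 ≈ 0.145.

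**Type I error.** Simulation of four cells of 25 with a simple list (20,000 runs per setting, g from 0 to 0.75) gave 0.049 to 0.050 without the term and 0.048 to 0.050 with it. If order is blocked within cells and the term is left out, the test becomes conservative: null rejection is about 2.5% to 3% at g = 0.5, and the term restores about 5%.

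**Direction at cluster level.** In the variant that gives 94.9%, an unmodelled g of 0.25 or 0.5 lowers power to 92.6% or 83.9%, and one further df changes it by under 0.5 point. Because this variant does not reproduce 89%, only the direction should be used.

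**The case against.** The strongest reply is that nothing is broken. Randomised order already protects the comparison, and the size of any gain rests on a g that the documents do not give. That stands. There are also reasons to expect g to be small. Go-NoGo activation is a subtraction within the session (correct NoGo trials on which the subject "responded correctly minus the parameter estimate of the Go stimuli on which the subject responded correctly"), and neutral and cocaine Stroop blocks alternate within each run, so additive session-wide shifts cancel. Only a change in the task contrast itself remains. A mock scan comes first, the Stroop task is also used at baseline and has a practice sequence, and the Compensation section pays controls for tasks at a practice scan. If g is below about 0.10 to 0.15, the term gains nothing and may lose a fraction of a point.

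It is also fair that silence is weak evidence. The form asks for language that non-scientists can follow, the covariate list is open, and the procedures table and uploads are not visible. The term may be intended but unwritten.

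A reader might go further and infer that the drug effect is confounded with session, that false positives are inflated, or that the stated 89% power is refuted. The documents do not support any of these. Order is randomised, type I error stays near 5% under a simple list and falls under a blocked one, and the calculations here do not test the 89%.

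What survives is that the trial randomises a factor which its described analysis does not use, and that using it is nearly free.

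**Conclusion.** The point holds as a low-priority improvement in precision. No order or session term is named, and omitting it causes neither bias nor excess type I error. At d = 0.57, which the plan itself discounts, modelling order recovers about 2, 8 and 15 points of power at g = 0.25, 0.5 and 0.75. At the planning d = 0.25 it recovers at most 3.3 points, so the term does not make a single two-cell contrast adequately powered. The conclusion assumes a common session effect across cells and equal residual variance, and it applies to one contrast in one region. The possible loss, 0.4 to 0.8 points when g is zero, is small beside the possible gain, but the gain is conditional on an effect that nobody has yet measured in this trial.

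**What to change.** State in the Statistical Analyses that every second-level drug-minus-placebo model includes order as a regressor, coded +1 (drug first) and −1 (placebo first), so that the drug effect is averaged over orders. If both scans enter a repeated-measures model, include session number (1 or 2) instead, because a sequence main effect alone does not remove session variance. If the term is already intended, one sentence saying so is enough.

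The cost is that sentence, one degree of freedom and the chance-imbalance cost worked out above. Whether the term fits within the allowance of up to four covariates is not shown, since urine status on two days may use several of them, but the effect on power is trivial either way. No new data or visits are needed, and the term can be added after enrolment has begun.

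An order-by-group term, in case users and controls change differently between sessions, is an optional sensitivity analysis costing up to 3 further df across four cells. Blocking order within cells is also optional. It should not be used without the order term, because the test is then conservative. The protocol should say which kind of list is used.

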
3. * Describe the study's specific aims or goals. Use lay language whenever possible.

Specific Aim 1. To examine the interaction of the serotonin receptor (5-HTR) type-2C Cys23Ser single nucleotide polymorphism (SNP) and a 5-HT2AR antagonist on the functional circuitry underlying impulsive action. We will test the hypotheses that 1) cocaine-dependent subjects displaying the Ser23 5-HT2CR genotype will show the highest fMRI activation and 2) greatest reduction in fMRI activation following the 5-HT2AR antagonist mirtazapine related to levels of impulsivity (Go- NoGo task) relative to controls with the Ser23 polymorphism, cocaine users without the polymorphism, and controls without the polymorphism, supporting a functional balance between 5-HT2AR:5-HT2CR in impulsivity in this patient population.

Specific Aim 2. To examine the interaction of the 5-HT2CR Cys23Ser SNP and a 5-HT2AR antagonist on the functional circuitry underlying cue reactivity. We will test the hypothesis that a functional balance between 5-HT2AR:5-HT2CR in cue reactivity exists in that 1) cocaine-dependent subjects displaying the Ser23 5-HT2CR genotype will present the highest fMRI activation and 2) greatest reduction in fMRI activation following the 5-HT2AR antagonist mirtazapine in the attentional bias task relative to controls with the Ser23 polymorphism, cocaine users without the polymorphism, and controls without the polymorphism.

Specific Aim 3. To explore the effective connectivity involved in the 5-HT2AR:5-HT2CR homeostasis impulsive action and cue reactivity. We will employ effective connectivity analyses using fMRI-based DCM to test the hypothesis that mirtazapine reduces impulsivity (Go-NoGo) and cue reactivity (attentional bias) greater in cocaine dependent subjects with the Ser23 polymorphism compared to controls with the Ser23 polymorphism, cocaine users without the polymorphism, and controls without the polymorphism through an increased prefrontal cortex-striatum ("top-down") connectivity.

Exploratory Aim. To explore interactions between other 5-HT2CR SNPs and brain activation after a 5-HT2AR antagonist. This exploratory analysis will examine other 5-HT2AR and 5-HT2CR polymorphisms that may need to be included as covariates in the analysis of the relationship between functional imbalance between 5-HT2AR and 5-HT2CR in the prefrontal-striatal-thalamic circuitry.

4. * Describe the scientific benefit or importance of the knowledge to be gained:

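### The 89% power is a whole-brain, any-cluster figure under random-sign effects; it is not power for a d = 0.25 group difference in the circuit the aims name

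*Combined protocol and SAP*

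**What the plan says.** The calculation is in Study Procedures, item 6, under fMRI Power Analysis. It is the only quantitative justification for 25 per group.

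- **Signal model:** "brain signals are modeled by continuously distributed Gaussian kernels of random height", with a width set in proportion to the field smoothness W. The kernel's standard deviation σ corresponds to signal height. "The new process representing signal+noise has zero mean and variance" 1 + σ².
- **How d enters:** signal height is set to the voxel t value implied by d. The within-group pilot effect of 0.83 converts to 0.57 between groups, which the plan regards as probably inflated. "Therefore for fMRI power analysis we have conservatively used a more modest effect size of 0.25".
- **Test:** family-wise-error-corrected, two-tailed α = 0.05 at cluster level; 188,579 voxels; W = [4.9 4.9 4.3]; f = 0.909; u = 4.5; k = 23; up to four covariates.
- **Result:** "a sample size of 25 subjects in each group would achieve a power of at least 89 percent" for the Go-NoGo between-group comparison, with still higher power expected for the Attentional Bias task.

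Aim 1 predicts that cocaine-dependent Ser23 subjects will show the "greatest reduction in fMRI activation following the 5-HT2AR antagonist mirtazapine related to levels of impulsivity", and Aim 2 predicts the same for cue reactivity. The hypothesis statement places the effect in a prefrontal-striatal-thalamic circuit and plans both a whole-brain voxelwise analysis and a region-of-interest analysis. No power is given for the region analysis.

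**The concern.** A reader who sees d = 0.25, 25 per group and 89% will take it that the design detects a quarter-SD group difference nine times in ten. An ordinary two-sample comparison of that size has far less power, and a whole-brain correction makes the test of a local effect harder, not easier. The explanation is that d = 0.25 is not a fixed difference at a location. It sets the spread of positive and negative effects assumed to exist throughout the brain. No circuit, circuit volume or predicted direction enters the calculation.

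Two things are at stake. A cluster outside the circuit counts towards the 89% but supports neither aim. And a null result could be read as evidence against a d = 0.25 difference that the study would usually miss.

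**Working it through.** **Inputs from the plan.** n = 25 per group; d = 0.25; R = 188,579 voxels; W = [4.9 4.9 4.3]; f = 0.909; u = 4.5; k = 23; two-tailed α = 0.05. With four covariates, df = 50 − 2 − 4 = 44.

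**Assumptions.** The plan cites its equations without printing them. I use t = d√(n/2) and the standard random-field cluster formulas below.

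**1. Signal SD.** σ = 0.25 × √12.5 = 0.884. Cutting n to 23 to allow for the covariates gives 0.25 × √11.5 = 0.848.

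**2. Reproducing k = 23.** R/ΠW = 188,579/103.243 = 1,826.6. For a t-field with v = 44:

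- E{m} = 1,826.6 × (4 ln 2)^1.5 (2π)^−2 (1 + u²/v)^(−(v−1)/2) [((v−1)/v)u² − 1] = 1.171
- E{N} = R × P(T44 > 4.5) = 4.65
- β = (Γ(2.5) E{m}/E{N})^(2/3) = 0.482
- P(size ≥ 23) = exp(−β × 23^(2/3)) = 0.0202
- P(at least one such cluster) = 1 − exp(−1.171 × 0.0202) = 0.0234

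At k = 22 the last value is 0.0262. So 23 is the smallest extent that holds 0.025 per tail, and the plan's k is reproduced.

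**3. Power in the plan's model.** Signal plus noise lowers the effective threshold and widens the field:

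- u′ = u/√(1 + σ²) = 4.5/√1.781 = 3.372
- W′ = W√[(1 + σ²)/(1 + σ²/(1 + f²))], so ΠW′ = 143.9
- E{m} = 11.08, P(size ≥ 23) = 0.176, power in one direction = 1 − exp(−11.08 × 0.176) = 0.857
- either direction = 1 − (1 − 0.857)² = 0.980

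The Gaussian-field rows use E{m} = (R/ΠW′)(4 ln 2)^1.5 (2π)^−2 (u′² − 1) exp(−u′²/2).

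| Convention | σ | One direction | Either direction |
|---|---|---|---|
| t-field, df 44 | 0.884 | 0.857 | 0.980 |
| t-field, df 44 | 0.848 | 0.800 | 0.960 |
| Gaussian, u = 4.06 (z-equivalent of t = 4.5) | 0.884 | 0.949 | 0.997 |
| Gaussian, u = 4.06 | 0.848 | 0.916 | 0.993 |
| Gaussian, u = 4.5 read as z | 0.884 | 0.603 | 0.843 |
| Gaussian, u = 4.5 read as z | 0.848 | 0.518 | 0.768 |

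The stated 89% lies inside this range. The closest variant tried gives 0.886, counting one tail, but it uses a back-solved threshold (4.108) that the plan does not state. Limiting the same random-sign model to part of the brain (t-field, σ = 0.884, one direction) gives 0.385, 0.177 and 0.093 for 25%, 10% and 5% of the volume. Only the any-cluster, whole-brain event comes near 89%.

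**4. A fixed effect in one region.** Two-sample noncentral t, df 44, two-sided 0.05, ncp = d√12.5, with d defined on the region mean:

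| d | ncp | Power |
|---|---|---|
| 0.25 | 0.884 | 13.9% |
| 0.57 | 2.015 | 50% |
| 0.81 | 2.864 | 80% |

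These are before any correction for the number of regions. A single voxel with true d = 0.25 exceeds t = 4.5 with probability P(T44(0.884) > 4.5) = 0.0006.

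**5. Taking 89% at face value.** With a Poisson count of clusters spread in proportion to volume, λ = −ln(1 − 0.89) = 2.21. The circuit's share of the volume is not given; I assume 10–30%.

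| Tails counted in the 89% | P(predicted-direction cluster in the circuit) | 10% share | 30% share |
|---|---|---|---|
| One | 1 − exp(−2.21 × share) | 20% | 48% |
| Both | 1 − exp(−2.21 × share/2) | 10% | 28% |

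**6. Cross-check by simulation.** In 400 smooth fields of about 188,000 voxels, with a uniform d = 0.25 in 2–25% of the volume (assumed), a qualifying cluster inside that region appeared in 5–38% of fields at u = 4.06 and in 0.5–7% at u = 4.5 read as z.

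**The case against.** The plan is open about its model. It states the zero mean, the random height, the whole-brain search volume and the two-tailed α. It attaches the 89% to a between-group activation comparison, and a whole-brain voxelwise analysis is one of the two planned. It never says in words that 89% is the power for the circuit. All of that stands, and it makes this a matter of what the figure means rather than an arithmetic error.

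Four stronger readings are tempting, and the documents do not support them.

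- **That the 89% is wrong.** k = 23 reproduces, and 89% falls inside the range of reconstructions. Without the printed equations it cannot be shown to be wrong as an omnibus figure.
- **That it counts clusters in either direction.** The plan says only that α is two-tailed. The closest numerical match counts one tail. That is why step 5 gives both readings.
- **That 0.25 is not a conservative input.** One might note that voxels crossing a high threshold have larger true effects than 0.25. But that conditions on crossing. Compared like for like inside the plan's model, 0.25 (σ = 0.884) is plainly more cautious than 0.57 (σ = 2.015), so the plan's word can stay.
- **That 14% is the power of the planned region test.** It is a scenario value. Averaging over voxels changes the noise, so a voxel-level d need not equal the d of the region mean.

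What remains is that the only power offered for 25 per group is labelled with an effect size that most readers will take as a fixed group difference, and neither the location nor the direction in the aims enters the calculation.

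**Conclusion.** The point holds as a matter of interpretation. As presented, the stated power does not justify 25 per group for a d = 0.25 difference in the hypothesised circuit. For that effect in a single prespecified region the design has about 14% power, so it would miss the effect about 86% of the time.

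The random-sign, whole-brain signal model is in the plan's own text. That success means any cluster anywhere is inferred from the reconstruction. The 14% rests on d being defined on the region mean and on an uncorrected two-sided 0.05. The 20–48% and 10–28% ranges rest on the assumed circuit share and on clusters falling in proportion to volume. No assumed share brings the circuit-level figure near 89%.

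**What to change.** In the fMRI Power Analysis paragraph:

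1. Restate 89% as the probability of at least one suprathreshold cluster anywhere in the search volume when random-sign effects with SD d = 0.25 exist throughout it, and state whether one tail or both were counted.
2. Beside it, give region-level power for the between-group difference in drug-minus-placebo change, with d defined on the region mean: about 14% at d = 0.25, 50% at d = 0.57 and 80% at d = 0.81, before correction for the number of regions.
3. State that a null result does not rule out a d = 0.25 difference.
4. Apply the same description to the statement that power will be greater for the Attentional Bias task.

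The cost is rewording one paragraph and a less favourable stated power. Enrolment and procedures do not change.
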